Supervised treadmill exercise program. Based on recommendations from clinical practice guidelines and evidence from clinical trial data, our supervised treadmill exercise intervention is a high-intensity exercise regimen (43,44,70). Supervised exercise will be delivered three times weekly for six months. In week one, participants will be asked to exercise on the treadmill for 15 minutes per session (excluding rest periods). Exercise duration will be increased by five minutes per session each week until 50 minutes of exercise per session is achieved (42,43,70). At this point, exercise intensity will be increased by alternately increasing treadmill speed and treadmill grade. Exercise intensity will be selected to ensure that participants experience ischemic leg symptoms within five minutes after onset of exercise. Participants will be asked to continue walking until they achieve leg symptom severity of “4 or 5” on a visual analog pain scale ranging from 1 to 5 (43,70). In the subset of participants without leg symptoms (i.e. those with asymptomatic PAD), participants will be asked to exercise to achieve a Borg Rating of Perceived Exertion (RPE) score of 12-14 (71-75). Participants may be asked to participate in up to three focus groups to discuss their experience in the study. We will ask consecutive patients who finished with the TELEX study if they would be willing to participate in a focus group, starting with the most recent finishers and working backwards. Participants would be asked to sign a separate focus group consent prior to participating. The purpose of the focus groups is to learn more about their experience with the study. The investigative team is specifically interested in barriers to participation in supervised treadmill exercise for people with PAD, because the investigative team is developing an exercise program for people with PAD that maximizes efficacy and is also acceptable and accessible for people with PAD.

Attention Control Group. Participants who are randomized to the non-exercising group will attend weekly one-hour educational sessions at Northwestern University for six months. These educational sessions are on topics of interest to the typical PAD patient and are led by physicians and other health care workers. Topics include pneumonia, nutritional supplements, and hypertension. Sessions do not include information about

PROTOCOL TITLE: Telmisartan Plus Exercise to Improve Functioning in PAD: The TELEX Trial

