11.0 Data and Specimen Management

11.1 Data management.

We will use REDCAP for data entry, via NUCATS.

11.2 Power Estimates/Calculations.

On October 31, 2019 investigators along with the DSMB and the study sponsor, NHLBI, agreed to change the primary aim to a single comparison of telmisartan (with and without supervised exercise) vs. placebo (with and without supervised exercise) due to difficulty recruiting participants for the trial who were not already taking an ACE inhibitor or an angiotensin receptor blocker. Although the investigators will still aim to recruit as many participants as possible (up to the originally proposed sample size), this change in primary aim provides statistical power for a sample size of 112 participants. Power calculations still take into account an anticipated 10% drop-out rate at 6-month follow-up, i.e., we expect to have approximately 25 participants per group (i.e. 100 overall) completing the 6-month follow-up.

PAD participants will be randomized to one of four study groups:

Group A: telmisartan + supervised exercise therapy;

Group B: telmisartan + a “no exercise” control group;

Group C: placebo + supervised exercise therapy; and

Group D: placebo + a “no exercise” control group.

For our revised Primary Aim, we will determine whether Group A+B improves six-minute walk performance at 6-month follow-up, compared to Group C+D, stratified by the exercise status. 50 PAD participants in each group provides 80% power to detect a minimum difference of 0.566 standard deviations (SD) between Groups A+B and C+D in changes of six-minute walk performance, using a two-sided two-sample t-test with a significance level of 0.05. As a sensitivity analysis, the following table summarizes the power for testing the primary aim with different total numbers of enrolled participants.

PROTOCOL TITLE: **Telmisartan Plus Exercise to Improve Functioning in PAD: The TELEX Trial**

#total patients	112	116	120	128
Power for detecting 0.566 SD	80%	82%	83%	85%

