In our SILC and GOALS trials (43,60), the observed differences in change of six-minute walk performance at 6-month follow-up between the intervention and control groups were 0.70 SD and 0.78 SD, respectively. In our SILC and GOALS trials, these observed differences represented a difference in six-minute walk change of 40 meters between the intervention and control groups (43,60), a clinically meaningful difference (79). Thus, we have adequate power for detecting similar or slightly smaller difference in the Primary Aim.

For Secondary Aim 1, we will determine whether Group A achieves greater improvement in six-minute walk at 6-month follow-up, compared to Group B and Group C, respectively. 25 participants in each group provides 70% power to detect a minimum difference of 0.72 SD between Groups A and B and between Groups A and C, respectively, in change of six-minute walk performance, using a two-sided two-sample t-test with a significance level of 0.05. For our Secondary Aim 2, we will determine whether Group B improves maximal treadmill walking, the WIQ, and the SF-36 PF score at 6-month follow-up, compared to Group D. The 25 PAD participants in each group also provide 70% power to detect a minimum difference of 0.72 SD.

For our Secondary Aim 3, we will determine whether Groups A+B combined improves maximal treadmill walking distance, the WIQ, and the SF-36 functioning score, compared to Group C+D combined, stratified by exercise status. 50 PAD participants in each group provides 80% power to detect a minimum difference of 0.566 SD between Groups A+B and C+D using a two-sided two-sample t-test with a significance level of 0.05. Thus, we have adequate power to detect effect sizes similar to the effect size in 6-minute walk distance in SILC and GOALS for all three Secondary Aims.

For Tertiary Specific Aim 1, we will determine whether Group B achieves greater improvement in maximal treadmill walking distance, the WIQ, and the SF-36 functioning score, compared to Group D. For Tertiary Specific Aim 2, we will determine whether Group A achieves greater improvement in maximal treadmill walking distance, the WIQ, and the SF-36 functioning score, compared to Group B and Group C, respectively. 25 participants in each group provides 60% power to detect a minimum difference of 0.64 SD between Groups A and B and between Groups A and C, respectively, using a two-sided two-sample t-test with a significance level of 0.05.

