Statistical Analyses. Analyses will be performed according to the intention to treat principle. Data will be analyzed according to each participant's originally assigned group, irrespective of whether the participant adheres to the assigned group. For the Primary Aim, we will use analysis of covariance (ANCOVA) to compare changes in six-minute walk performance at 6-month follow-up between Group A+B combined and Group C+D combined, adjusting for study site (Northwestern or Tulane) and randomization to exercise status. For our Secondary Aim 1 and our Secondary Aim 2, we will use two sample two-tailed t-tests to compare changes in six-minute walk at 6-month follow-up between Groups A and B, between Groups A and C, and between Groups B and D, all stratified by study site. For our Secondary Aim 3, we will use ANCOVA to compare changes in maximal treadmill walking distance, the WIQ, and the SF-36 physical functioning score between Groups A + B vs. Groups C + D, adjusting for study site and randomization to exercise. For our Tertiary Specific Aim 1, we will use t-tests to compare maximal treadmill walking distance, the WIQ, and the SF-36 functioning score, between Groups B and D stratified by study site. For our Tertiary Specific Aim 2, we will use t-tests to compare maximal treadmill walking distance, the WIQ, and the SF-36 physical functioning score, between Groups A and B, and between Groups A and C, respectively, also stratified by study site. For our Exploratory Aims, we will use ANCOVA to compare changes in gastrocnemius muscle biopsy measures of each muscle measure between Groups A+B vs. C+D adjusting for study site and randomization to exercise. We will also compare Groups A, B, and C, respectively vs. Group D using two sample t-test stratified by study site. When the distribution of changes in the primary, secondary, and exploratory outcomes of interest is "very non-Gaussian", we will either apply appropriate transformation before conducting t-tests or perform Wilcoxon rank-sum test for the comparisons. Prior to analyses, we will also check the potential imbalance of socio-demographic factors and prognostic factors (such as age, sex, race, baseline outcome measure, ABI, BMI, smoking status, comorbidities, and relevant medication use) between the two groups using t-tests for continuous factors and chi-square test for discrete factors. If there is any indication of major imbalance in these factors or baseline variables are associated with the change in outcome of interest, we will perform ANCOVA to further adjust for the relevant baseline factors as potential confounders, in addition to randomization to exercise status and site, for two-group comparison. Similar analysis will be performed for exploratory aims. In the analysis for the secondary, tertiary and exploratory aims, we will not adjust for multiple testing. However, we will report all the results regardless of their significance to present an overall picture of the treatment effect of

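### For non-normal changes the primary ANCOVA gives way to an open choice of fallback tests with no stated exercise or site strata, trigger or named transformation; one stratified rank test would do better

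*Combined protocol and SAP*

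**What the plan says.** Section 11.2, Statistical Analyses, compares telmisartan with placebo for the Primary Aim by ANCOVA of the six-month change, "adjusting for study site (Northwestern or Tulane) and randomization to exercise status". The power text in the same section describes the primary comparison as "compared to Group C+D, stratified by the exercise status".

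The fallback opens with "When the distribution of changes in the primary, secondary, and exploratory outcomes of interest", so it covers the primary outcome. If those changes are very non-Gaussian, "we will either apply appropriate transformation before conducting t-tests or perform Wilcoxon rank-sum test for the comparisons". That sentence mentions neither exercise nor site, and it speaks of t-tests although the primary test is an ANCOVA.

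A later sentence on baseline imbalance keeps the design factors explicitly ("in addition to randomization to exercise status and site, for two-group comparison"). It is triggered by imbalance or prognostic association, not by distributional shape.

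Section 11.4 blinds the interviewer who collects outcomes. Section 9.1 has the data management team send assignments to the pharmacy. Neither says who checks the shape of the changes, or whether that person is masked to drug.

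**The concern.** The method for the primary outcome depends on a judgement about the data. Four things are unstated: when the switch is made, which of the two tests follows, which transformation is used, and whether the design factors stay in. Changes can be negative, so a log or root also needs a shift constant.

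Three things are at stake:

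- **Strata.** If exercise works and is left out of the test, its effect becomes noise in the drug comparison, and power is lost for no gain.
- **Open choice.** In a trial planned at exactly 80% power, the unnamed transformation could leave power below or well above plan.
- **Interpretation.** The plan judges clinical meaning in metres: "these observed differences represented a difference in six-minute walk change of 40 meters". A rank or transformed-scale test alone gives no such estimate.

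**Working it through.** **1. The plan's own figure.** Inputs from Section 11.2: 50 evaluable per pooled arm (25 per cell), 0.566 SD, two-sided 0.05. The noncentrality is 0.566 × √(50/2) = 2.83 and the critical value is t(98 df) = 1.984. Power is about Φ(2.83 − 1.984) = Φ(0.846) = 80%; the exact noncentral t gives 80.0%. The stated 80% reproduces.

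**2. Why dropping exercise costs power.** With balanced cells and an exercise effect of e within-cell SD, an unstratified test sees a pooled SD of √(1 + e²/4), while the drug estimate varies only with the within-cell SD. For e = 0.70:

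- inflation: √(1 + 0.49/4) = 1.059
- effective critical value: 1.984 × 1.059 = 2.10
- size: 2 × [1 − Φ(2.10)] = 3.6%
- power of the unstratified t-test: Φ(2.83 − 2.10) = Φ(0.73) = 77%

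This agrees with a simulated 76.5%. The test is valid but conservative.

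The values of e come from two earlier exercise trials, where the differences "were 0.70 SD and 0.78 SD, respectively". Here "Supervised exercise will be delivered three times weekly for six months", whereas by its reference title one of the two trials was home-based. The effect may therefore differ, so 0 and 0.35 SD are also shown.

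**3. Rank tests with and without strata.** Simulation: 40,000 runs per setting, 25 per cell, drug effect 0.566 SD, no site effect. The documents give no distribution for the changes, so the error shapes are assumptions. Figures are percentages at e = 0.74; the last two columns are size.

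| Errors | ANCOVA | Plain Wilcoxon | Rank test stratified by exercise | Size, plain | Size, stratified |
|---|---|---|---|---|---|
| Normal | 80.0 | 73.9 | 78.0 | 3.9 | 5.3 |
| t, 3 df | 83.3 | 92.2 | 96.4 | 2.8 | 5.1 |
| Lognormal, log-SD 0.5 | 80.3 | 86.9 | 92.7 | 2.8 | 4.9 |
| Lognormal, 0.75 | 81.0 | 95.3 | 98.9 | 2.4 | 5.0 |
| Lognormal, 1.0 | 82.9 | 99.1 | 100.0 | 1.5 | 5.1 |

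Power lost by the plain Wilcoxon against the stratified test, over e = 0.70 to 0.78:

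- normal: 3.7 to 4.6 points
- t3: 3.4 to 4.6
- lognormal 0.5: 5.0 to 6.5
- lognormal 0.75: 3.1 to 4.0
- lognormal 1.0: 0.9 to 1.3

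At e = 0.35 the loss is 0.1 to 1.2 points. At e = 0 there is none.

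**4. The open choice.** Under t3 errors and e = 0.74, a t-test after a shifted log has power 57%, 72% or about 75% for shifts of 0.1, 1 or 2 SD. After arcsinh it has 91.5%, against 92.4% for the Wilcoxon in the same run.

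With no exercise effect, across six heavy-tailed shapes (t with 4, 3 and 2.5 df, Laplace, two contaminated normals), the Wilcoxon leads by:

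- arcsinh: 1 to 3 points
- Yeo-Johnson: about 7 to 14 points
- log with a shift of one scaled median absolute deviation: 18 to 35 points

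Under moderate skew (lognormal 0.5) the order changes: log-t 86 to 93%, Wilcoxon 86 to 87%, arcsinh-t 83 to 85%. No unstratified option wins throughout.

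**5. Selection.** Taking the smallest p of ANCOVA, log-t (shift 1 SD) and Wilcoxon gives type I error of 4.8 to 6.1% at e = 0.70 to 0.78, 6.1 to 6.8% at 0.35 and 6.9 to 7.6% at 0. Over six tests it is 4.9 to 6.4% at 0.70 to 0.78 and 7.0 to 8.0% at 0.

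**6. The proposed procedure.** Assumptions: 80/20 site split, 0.3 SD site effect, and a switch if Shapiro-Wilk p < 0.01 on changes centred within exercise-by-site with drug arms pooled. Switching to the rank test stratified by exercise and site gives type I error of 4.6 to 5.0%. Power is 79 to 80% (normal), 94 to 95% (t3) and 92% (lognormal 0.5).

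**The case against.** The strongest reply is that a sensible statistician would read the fallback in context. The primary comparison has just been described as adjusted for site and exercise, and the power text stratifies it by exercise, so the strata may be meant to carry over. That is possible, and one sentence would settle it; as written, it is not stated. The strata loss also needs a working exercise effect and shrinks to nothing without one.

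A reader might infer from the shifted-log figures that the two options differ by some 17 to 35 points under heavy tails, or that a transformed t-test falls below both ANCOVA and 80%. The documents do not support that. They name no log and ask for an appropriate transformation, and a log is a poor choice for symmetric heavy tails. With arcsinh the gap is about 1 to 3 points and power exceeds ANCOVA. The same holds if strata are kept: under t3, log ANCOVA has 74 to 75% and arcsinh ANCOVA 92 to 93%, against 95 to 96% for the stratified rank test.

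A reader might also infer that the plan inflates type I error. Each fixed option is valid. Inflation needs selection on results, which no section says is intended, and the lack of a masked shape check is an inference from silence.

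Finally, nothing shows that the switch will be triggered, and Section 9.1 allows up to 240 participants, so absolute power could be higher. These points limit the size of the concern. They do not supply the missing rule, nor make an unstratified rank test as good as a stratified one.

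**Conclusion.** The concern holds in limited form. A rank fallback is sound in itself: under the heavy-tailed and skewed shapes tried, even the plain Wilcoxon beats the ANCOVA. The defect is that the replacement for the primary test is open and, read literally, drops the design factors.

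The firmest numerical result is the strata loss: about 1 to 6.5 points with size about 1.5 to 4% at an exercise effect of 0.70 to 0.78 SD, about 0 to 1 point at 0.35 SD, and nil without an effect. The gap between the two fallback options, about 1 to over 30 points under heavy tails, measures what the wording leaves open; it is not a property of the plan. The 6 to 8% type I error is a ceiling.

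All of this assumes 25 per cell, a drug effect of 0.566 SD and error shapes that the documents do not give. The change is worth making before unblinding, but the primary analysis as planned is not invalid.

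**What to change.** - Keep the ANCOVA adjusted for site and exercise as the primary test.
- Replace the transformed-t/Wilcoxon pair with one rank test stratified by exercise and site (van Elteren or rank ANCOVA), as the sole fallback or as a sensitivity analysis.
- If a switch is kept, fix a numerical trigger before unblinding. Apply it to changes centred within exercise-by-site, with drug arms pooled and drug codes masked.
- Report the adjusted difference in metres in either case. For scale, 40 m at 0.70 to 0.78 SD implies an SD of 40/0.70 = 57 m to 40/0.78 = 51 m, so 0.566 SD is about 29 to 32 m.
- If the strata were always meant to carry over, say so.

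The cost is minor SAP wording, a few lines of code, and someone without drug codes to run any trigger. Used on normal data, the stratified rank test has about 2 points less power than the ANCOVA (78.0 against 80.0%); a trigger largely confines that loss. Dropping the switch altogether is optional. It is simpler, but leaves the ANCOVA's 83% as the primary result under t3 errors, where the stratified rank test has about 96%.

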8.0 Study Endpoints

The primary study endpoint is the six-month change in the six minute walk data.

Secondary study endpoints include a) six-month change in treadmill walking performance; b) six-month change in Walking Impairment Questionnaire; c) six-month change in health-related quality of life, measured with the Short-Form-36 Physical Functioning Score.

Exploratory study endpoints are change in calf muscle biopsy measures, consisting of calf muscle biopsy-obtained satellite cell number, Type I muscle fiber composition, PPAR δ , PGC-1 α , AMPK quantity and activity, and relative gene expression of PPAR δ , PGC-1 α , AMPK, FOXO3A, and SIRT-1.

Additional exploratory outcomes are a) six-month change in usual-paced four-meter walking velocity; b) six-month change in fast-paced four meter walking velocity; c) six-month change in the short physical performance battery (SPPB) score.

All data will be collected at baseline and at the 6-month follow-up visit.

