9.0 Procedures Involved

[figure not shown]
9.1 Study design.

STUDY OVERVIEW. We will randomize a minimum of 112 and up to 240 participants with PAD to one of four parallel study arms: Group A: telmisartan + supervised exercise; Group B: telmisartan + a "no exercise"

PROTOCOL TITLE: Telmisartan Plus Exercise to Improve Functioning in PAD: The TELEX Trial

control group; Group C: placebo + supervised exercise; and Group D: placebo + a “no exercise” control group. Participants will undergo baseline testing, a two-week study run-in period, six months of their assigned study group, and six-month follow-up testing (Figure 2).

Figure 2. Overview of the Telmisartan Trial Design.

Telephone screening.

Initial eligibility criteria will be assessed by telephone via a telephone call script. The study will be described to the potential participant and the participant will be asked a series of eligibility questions to determine whether they qualify for a baseline study visit. If they qualify for a baseline visit, we will collect their name, address, telephone number(s), email address, date of birth, gender, race, and ethnicity.

Baseline testing.

Participants will be asked to come to Northwestern Memorial Hospital at baseline for the purposes of providing informed consent. In addition, at the baseline study visits, we will obtain the ankle brachial index (ABI) measurement, to ensure they are eligible for the study. If the participant meets initial eligibility requirements, we may mail a letter to the participant’s physician to notify him or her of their patient’s involvement with the study, unless the participant does not have a physician or requests that we do not notify their physician. We will administer study questionnaires, such as the Walking Impairment Questionnaire and the Short-Form-36 Physical Functioning Score, to obtain information about their medical history. We will perform baseline physical functioning tests including the six-minute walk test, chair stands, balance testing, and the treadmill walking performance test. We will take a blood sample, measure participants’ height and weight, and measure the blood pressure in their arm. In addition, participants will be asked to undergo a calf muscle biopsy at baseline. Participation in the calf muscle biopsy is optional. Participants will be asked to have a physical examination prior to randomization. Baseline study visits will be performed over multiple days.

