
PROTOCOL TITLE: Telmisartan Plus Exercise to Improve Functioning in PAD: The TELEX Trial

telmisartan. In additional exploratory analyses, adjustment for multiple comparisons may be performed.

Analyses regarding missing data: If missing data due to participant dropout is missing completely at random, then the aforementioned analyses based on available data provide valid statistical inferences. When missing data due to dropout is not missing completely at random, we will perform several sensitivity analyses. Specifically, we will employ the multiple imputation approach to account for missing data at 6-month follow-up under the assumption of missing at random (91). We will perform additional sensitivity analyses to guard against the possibility of missing not at random using extreme value imputation, selection models and shared-parameter models (92).

11.3 Steps to secure data to maintain confidentiality during storage, use, and transmission.

First, all research assistants must complete training in protection of subject privacy and prevention of disclosure of identifying information.

Second, all data collection forms are maintained in a secure office space.

Third, our study databases are maintained in locked computer files or on secure hard-drives that are password protected; to which only authorized staff have access. [name] or a study manager must provide permission for programmers and research assistants to access study databases.

Fourth, a study identification number will be assigned to each participant. This identification number will be used to label blood specimens, for example. In addition, most pages of our data collection forms will have only the study identification number listed (and not the participant's name, for example).

11.4 Quality Control.

Health interviewers will be trained by a senior coordinator and certified by [name] in each data collection element, using a detailed checklist. Health interviewers are rigorously evaluated for adherence to protocol, delineated in our manuals, prior to beginning data collection. They are re-certified approximately every six months by a project manager or [name]. When deficiencies are identified, interviewers undergo additional training and re-assessment. Ten percent of participants are randomly identified for quality control. This subset has their ABI measured twice by

PROTOCOL TITLE: Telmisartan Plus Exercise to Improve Functioning in PAD: The TELEX Trial

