independent examiners and may have a split sample of muscle tissue (i.e. two samples from the same participant) sent for analyses. The second muscle sample is designated an arbitrary identification number to which the technician is blinded. Thus, quality control is monitored continuously. [name] meets with the exercise physiologist(s) to review individual participant's progress.

Blinding for data collection. The health interviewer collecting outcome data will be blinded to the study group assignment. Participants are instructed not to reveal their group assignment. If a participant reveals their group assignment, data collection is immediately stopped and another certified health interviewer is paged or contacted by telephone to continue the visit.

Missing Data. Missing data may occur when some participants are lost to follow-up. First, we will make every effort to ensure that participants return for 6-month follow-up. We will use proxies to help us locate participants we are unable to reach and we will mail letters to participants who do not respond to our telephone contacts. We will encourage participants who do not adhere to their assigned groups to return for six-month follow-up. We will provide transportation and monetary incentives. Thus, we anticipate that most participants will complete six-month follow-up data collection. Second, we will record the reason for dropout for each participant. If dropout is completely at random, then the aforementioned analyses based on available data provide valid statistical inferences. When dropout is not completely at random, we will perform several sensitivity analyses. Specifically, we will employ the multiple imputation approach to account for missing data at 6-month follow-up under the assumption of missing at random (91). We will perform additional sensitivity analyses to guard against the possibility of missing not at random using extreme value imputation, selection models and shared-parameter models (92).

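### Analyses of all randomised participants run only if dropout is judged not completely at random, yet the plan gives no criterion and data can never confirm complete randomness

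*Combined protocol and SAP*

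**What the plan says.** The Statistical Analyses paragraph of Section 11.2 states: "Analyses will be performed according to the intention to treat principle". It explains this as analysis by assigned group whatever the adherence. The primary analysis is an ANCOVA of six-month change in six-minute walk, pooled telmisartan arms against pooled placebo arms, adjusted for site and exercise assignment. Further baseline covariates (the list includes the baseline outcome, ABI and comorbidities) enter if there is major imbalance or if they are associated with the change.

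On missing data, Section 11.2 and the Missing Data paragraph of Section 11.4 give the same two-branch rule. In Section 11.4 the first branch reads: "If dropout is completely at random, then the aforementioned analyses based on available data provide valid statistical inferences". The second branch, in Section 11.2, reads: "When missing data due to dropout is not missing completely at random, we will perform several sensitivity analyses". Those analyses are multiple imputation under missing at random and, for missing not at random, extreme-value imputation, selection models and shared-parameter models. Section 11.4 adds that the reason for each dropout is recorded.

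On the endpoint schedule, Section 8.0 says: "All data will be collected at baseline and at the 6-month follow-up visit".

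**The concern.** The rule asks the analyst to decide which missingness mechanism holds before deciding whether to run any missing-data analysis. Observed data can sometimes show that dropout is not completely at random. They cannot show that it is. Failure to find a pattern among a handful of dropouts is weak evidence, and dropout that depends on the unseen 6-month walk cannot be tested at any sample size. The plan names no test, threshold, decision-maker or timing, and no rule links the recorded reasons to the decision.

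A participant without a 6-month walk has no change score and leaves the primary model. If dropout is judged completely at random, the rule as written calls for no analysis that includes these participants. The judgement could also be made after results by arm are known. Informative dropout is possible here: Sections 9.3 and 14.0 list hypotension, kidney problems and hyperkalemia as drug side effects. Section 9.1 has the run-in test tolerance at 20 mg, while the dose after randomisation may rise to 80 mg as tolerated, so the run-in does not exclude later drug-related dropout.

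**Working it through.** **Inputs from the documents.** Section 11.2: "this change in primary aim provides statistical power for a sample size of 112 participants", and "Power calculations still take into account an anticipated 10% drop-out rate at 6-month follow-up". The same section gives 50 completers per pooled arm, 0.566 SD, 80% power and two-sided 5%. Section 9.1: "We will randomize a minimum of 112 and up to 240 participants with PAD to one of four parallel study arms".

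**1. The plan's own figures.** A two-sample t-test with 50 per arm and 0.566 SD has power 80.0% (80.8% by the normal approximation), which matches the stated 80%. Dropout: 112 × 0.10 = 11.2, leaving 100.8 completers, which matches the plan's figure of about 100. At the ceiling, 240 × 0.10 = 24 dropouts and 216 completers.

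**2. What a significance check could detect.** The plan names no check. As an illustration only, assume a two-sided 5% t-test of one baseline variable, dropouts against completers:

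| True baseline difference | 11 vs 101 (N = 112) | 24 vs 216 (N = 240) |
|---|---|---|
| 0.3 SD | 16% | 28% |
| 0.5 SD | 35% | 64% |
| 0.8 SD | 71% | 96% |

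Power of 80% needs a difference of about 0.90 SD at N = 112 and about 0.61 SD at N = 240.

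**3. What a comparison of dropout by arm could detect.** With 56 per pooled arm and 11 dropouts in total, Fisher's exact test gives p = 1.00 for a 6:5 split, 0.53 for 7:4, 0.20 for 8:3 and 0.053 for 9:2. Only 10:1 or 11:0 falls below 0.05.

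**4. How far the completer estimate could move.** Let dropouts' mean six-month change be m SD worse than completers' in both arms. The mean over everyone randomised to an arm is the completer mean minus m × (dropouts / 56). The completer difference is therefore off by m × (a − b)/56, where a and b are the dropouts in the two arms. The values of m (0.5 to 1.0) and the splits are assumptions; the documents give neither.

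- 6:5 split: 0.5 × 1/56 = 0.009 SD; 1.0 × 1/56 = 0.018 SD.
- 8:3 split: 0.5 × 5/56 = 0.045 SD; 1.0 × 5/56 = 0.089 SD.

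Section 11.2 equates 40 m with 0.70 and 0.78 SD, so one SD is 40/0.70 = 57 m or 40/0.78 = 51 m. The larger 8:3 figure is then about 5 m. As a share of 0.566 SD, the 8:3 range is 8% to 16% (0.045/0.566 and 0.089/0.566) and the 6:5 range is 2% to 3%. The standard error of the difference with 50 per arm is √(1/50 + 1/50) = 0.20 SD, so even 0.089 SD is under half a standard error.

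Steps 2 and 4 measure different things. Step 2 concerns a difference in a baseline variable; step 4 concerns a difference in the outcome. One cannot be read off from the other.

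**The case against.** The strongest reply is the covariate rule in Section 11.2. Dropout related to a baseline variable biases the mean change only if that variable is also related to change, and that is when the rule adds it. With a single follow-up value, an available-data ANCOVA containing those covariates is valid under missing at random given them, and imputing from the same variables adds little. This stands as far as it goes. But the rule depends on what the data happen to show, and it does not reach adherence or tolerability after randomisation.

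The plan also limits the problem in advance. The run-in removes intolerant and non-adherent people, exercise assignment is balanced across the pooled drug arms, and Section 11.4 describes active retention. These make a large bias less likely. They do not justify omitting the check.

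Three stronger readings are tempting, and the documents do not support them.

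- A reader might infer that the condition turns the primary result into a completers-only one. It does not. Imputation is labelled a sensitivity analysis, so the primary ANCOVA uses available data whichever way the judgement falls.
- A reader might infer a contradiction with the intention-to-treat statement. Section 11.2 ties that principle to assigned group and does not claim that every randomised participant has an analysed value. This is a gap, not a contradiction.
- A reader might infer from the 35% power that informative dropout would be missed about 65% of the time. That would describe a test the plan does not specify; a judgement from recorded reasons fits the text equally well. The figure of about 11 dropouts also holds only at the minimum enrolment.

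The choice of methods for missing not at random is partly preference. With one post-baseline walk, selection and shared-parameter models lean heavily on assumptions that cannot be tested, but so does any such analysis, and extreme-value imputation is already planned.

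**Conclusion.** The concern holds in a limited form. Sections 11.2 and 11.4 make multiple imputation and every analysis under missing not at random conditional on a judgement that has no stated criterion and whose negative answer data can never confirm. Following the rule as written can leave the report with no analysis of all randomised participants. The primary model itself is unaffected by the condition.

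The likely size is modest: about 0.01 to 0.02 SD for a 6:5 split of 11 dropouts and 0.04 to 0.09 SD for 8:3, if dropouts' change is 0.5 to 1.0 SD worse. That could matter for a borderline result and would not overturn a clear one. The splits and outcome deficits are assumptions, and the detection powers rest on an assumed test. The core of the point, an undefined condition that cannot be confirmed, needs none of them.

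**What to change.** In Sections 11.2 and 11.4, delete the condition that dropout be not completely at random. Always report multiple imputation under missing at random for all randomised participants, alongside the primary ANCOVA. Put in the imputation model: drug, exercise, site, biopsy stratum, baseline walk, age, ABI and the adherence data already collected (monthly pill counts in Section 9.3; drug, exercise and education-session adherence in Section 12.0). Always report the planned extreme-value analysis too. A delta-adjusted tipping-point analysis by arm is an optional and more transparent extension.

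The cost is SAP wording and a little more analysis work. No new data are needed, and the sample size stays at 112.
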